6.4 Protocol Therapy Discontinuation

In addition to discontinuation from therapy related to toxicities as outlined above, a subject will also be discontinued from protocol therapy and followed per protocol under the following circumstances outlined below. The reason for discontinuation of protocol therapy will be documented in the EDC system.

- Documented disease progression
- Site investigator determines a change of therapy would be in the best interest of the subject
- Subject requests to discontinue protocol therapy, whether due to unacceptable toxicity or for other reasons
 - In a subject decides to prematurely discontinue protocol therapy (“refuses treatment”), the subject should be asked if he or she may still be contacted for further scheduled study assessments. The outcome of that discussion should be documented in both the medical records and in the eCRF.
- Female subject becomes pregnant
- Protocol therapy is interrupted for ≥ 12 weeks.
- A maximum of 24 continuous months of pembrolizumab (35 cycles) was administered.

6.5 Protocol Discontinuation

If a subject decides to discontinue from the protocol (and not just from protocol therapy) all efforts should be made to complete and report study assessments as thoroughly as possible. A complete final evaluation at the time of the subject's protocol withdrawal should be made with an explanation of why the subject is withdrawing from the protocol. If the reason for removal of a subject from the study is an adverse event, it will be recorded on the eCRF.

11: Archival tissue must be identified during screening and shipped prior to Day -21. If archival tissue or standard of care biopsy is not available, a standard of care biopsy will be performed. Please see SPM for additional details.

12: If a subject has a biopsy at progression as per standard of care, some of this tissue will be stored for research particularly directed at resistance.

13: The end of treatment visit should only occur when subjects permanently stop study treatment for whatever reasons (toxicity, progression, or withdrawal by the subject or investigator) and should be performed 30 days (\pm 7 days) after the last dose of treatment. Subjects who have an ongoing Grade \geq 2 adverse event (AE) at the time of discontinuation should have this visit continued until the AE resolves to \leq Grade 1 or baseline, deemed clinically insignificant, and/or until a new treatment starts, whichever is earlier.

14: [REDACTED]

8. BIOSPECIMEN STUDIES AND PROCEDURES

Summary Tables of Blood specimens

Type of biospecimen to submit	Mandatory or optional	When to submit	Collection tube description and/or additive (color of tube top)	Volume to collect per tube (number of tubes to be collected)	Blood product being processed and submitted by participating site	Additional processing required at site after blood draw?	Storage/ shipping conditions	Reason for submission (background/methodology section)
Blood for correlative research ([name] Lab) ^a	Mandatory	Pre-treatment Day -21, C1D1, C2D1, C3D1, EOT; See calendar above for additional details	EDTA (purple top)	10 ml (2)	Whole blood	No	Ambient temperature (DO NOT FREEZE)	Defined translational studies (Section 1.5)
Blood for somatic baseline	Mandatory	Pre-treatment Day -21	EDTA (purple top)	10 ml (1)	Whole blood	No	Frozen to HCRN	Stored for future somatic baseline testing

*CLM = Correlative Laboratory Manual

Summary Table of Tissue Specimens

Type of tissue biospecimen to submit	Mandatory	When to submit	Reason for submission (background/methodology section)	Where to find specific details for biospecimen submission
Formalin-fixed paraffin-embedded (FFPE) tissue blocks with corresponding H&E (OR unstained slides with corresponding H&E); archival or fresh biopsy	Mandatory	Prior to Day -21	CLM	CLM
Formalin-fixed paraffin-embedded (FFPE) tissue block with corresponding H&E (OR unstained slides with corresponding H&E)	Mandatory	At time of tumor recurrence during standard of care biopsy.	CLM	CLM

8.1 Whole Blood Collection

Please see Tables above and CLM for additional information regarding blood collection. Collection of these samples should occur Monday- Thursday.

8.1.1 Return of Genetic Testing Research Results

Since the results generated by the somatic baseline genetic testing included in this section are not currently anticipated to have clinical relevance to the patient or their family members, the genetic results will not be disclosed to the patients or their physicians. Sharing of research data with individual patients should only occur when data have been validated by multiple studies and testing has been done in CLIA-approved laboratories.

8.2 Tissue Collection Information

8.2.1 Pretreatment Tissue

Pretreatment tumor tissue must be submitted for this trial. Archived tumor tissue is sufficient and tissue collected as close as possible to study treatment is strongly encouraged. A documented attempt to locate and retrieve archival tissue should be made during screening. Please see the CLM for documentation form. If archival tissue is identified, it should be shipped prior to Day -21. If archival tissue is not available and a standard of care biopsy is not being performed, a research biopsy is required for study eligibility.

Submitted tissue samples will be analyzed for the following biomarkers:

- TOO assay
- Immune status using such assays as mismatch repair, microsatellite instability, mutational load, genomic profile, PD-L1, BIM-PD-1 expression, tumor infiltrating lymphocytes, and others
- Molecular pathways that are deemed to be relevant for prognosis or ability to predict outcomes from immune and/or radiotherapy

The rationale for these tissue studies is explained below.

8.2.2 Tissue from Standard of Care Biopsy at Progression

If a subject has a biopsy at progression as per standard of care, some of this tissue will be stored for research particularly directed at mechanisms of resistance such as but not limited to BIM/PD-1 expression, and CD3, CD8, granzyme B by IHC and other molecular markers in the PD-1 pathway.

8.3 Sample Analyses

8.3.1 MSI and Mutation Load

Recent data implicate the potential value of MSI (mismatch repair) status ([Le et al., 2015](#)) and mutation load ([Le et al., 2015](#); [Rizvi et al., 2015](#)) in predicting anti-PD-1/PD-L1 blockade. As described above, CUPs appear to have a relatively high proportion of tumors with high mutation load. MSI data are recently available on certain genomic profiles, which also provides information on alterations in hundreds of cancer-related genes and mutational load. Genomic testing is commercially available and has been obtained as part of clinical care in Mayo Clinic

patients to facilitate treatment options.

Given that genomic testing is often routinely ordered in clinical settings, some subjects may already have had the necessary analyses performed. Subjects who have had previous genetic results including MSI and mutation load must consent to permit use of those previous findings by the investigators and therefore not need additional genomic testing. If previous results are not available, subjects must consent to providing tissue for this analysis.

8.3.2 Tissue Expression of PD-L1 and Immune Markers

PDL1 expression is an important marker that has potential predictive value for pembrolizumab therapy. The density of markers of adaptive immunity such as CD3, CD8, FoxP3, and CD45RO infiltrating intratumoral/stromal tissue compartments have been associated with survival in patients with colorectal cancer, as we ([Yoon et al., 2012](#)) and others ([Galon et al., 2006](#); [Pages et al., 2005](#)) have shown. It is possible that adaptive immune markers in TILs, apart from PD-L1 expression, can have predictive value for immunomodulating agents ([Kluger et al., 2015](#)).

Pre-treatment tissue and tissue from standard of care biopsy at progression will be analyzed for multiple markers including PD-L1, CD3, CD8, FoxP3, CD45RO via IHC.

8.3.3 Soluble PD-L1

Release of inhibitory coregulatory proteins into the circulation may represent one mechanism by which tumors thwart immune responses. A collaborator in the current trial ([name] Laboratory) identified a soluble form of PD-L1 that retains immunosuppressive activity and is associated with aggressive renal cell carcinoma ([Frigola et al., 2011](#)). This lab developed an ELISA for quantification of PD-L1 in biological fluids. Soluble PD-L1 was detected in the cell supernatants of some PD-L1-positive tumor cell lines. Protein sequencing established that the measured soluble PD-L1 retained its receptor-binding domain and could deliver proapoptotic signals to T cells. Higher preoperative soluble PD-L1 levels were associated with larger tumors ($P < .001$), tumors of advanced stage ($P = .017$) and grade ($P = .044$), and tumors with necrosis ($P = .003$). A doubling of soluble PD-L1 levels was associated with a 41% increased risk of death ($P = .010$). These observations suggest that soluble PD-L1 may be detected in the sera of cancer patients and that it may systemically impair host immunity, thereby fostering cancer progression and subsequent poor clinical outcome.

Peripheral blood is collected for soluble PD-L1 analyses at the following 5 time points: (1) prior to treatment Day -21 (2) prior to treatment Cycle 1 Day 1 (- 5 days), (3) prior to treatment Cycle 2 Day 1 (- 5 days), (4) prior to treatment Cycle 3 Day 1 (first pembrolizumab after completion of RT' - 5 days) and (5) at the time of treatment discontinuation.

8.3.4 Tumor-Reactive CD11a^{high}PD-1^{high} CD8⁺ T Effector Population Following RT

T cell receptor (TCR) tetramers can detect tumor-specific immunity but have limitations. Both the down regulation of the TCR induced by persistent tumor antigen encounter and the weak affinity of CD8⁺ T cells for tumor antigens contribute to the underestimation of anti-tumor responses measured by tetramers. In addition, TCR tetramers are not capable of detecting CD8⁺ T cell responses to subdominant epitopes. Therefore, a novel method of detecting tumor-related T cell response is necessary in situations where the identity of tumor antigens are unknown or suboptimal to be detected by tetramers. CD11a expression is required in the rejection of tumors

([Schmits et al., 1996](#)). A collaborator laboratory recently established that the CD11a^{high} PD-1⁺ CD8⁺ T cell population represent tumor-reactive CD8⁺ T cells([Liu et al., 2013](#)). In addition, work from this lab determined that CD11a^{high} CD8⁺ T cells inside tumors are tumor-specific functional effector cells and that their function is enhanced by stereotactic ablative radiotherapy in PD-1 knockout mice([Park et al., 2015](#)). In the current study, we propose to investigate whether the CD11a^{high} PD-1⁺ CD8⁺ T cell population in GEJ cancer patients following the initiation of chemoRT plus pembrolizumab can identify tumor-related T cell response.

PBMCs and plasma will be collected at the following 5 time points: (1) prior to treatment Day - 21 (2) prior to treatment Cycle 1 Day 1 (- 5 days), (3) prior to treatment Cycle 2 Day 1 (- 5 days), (4) prior to treatment Cycle 3 Day 1 (first pembrolizumab after completion of RT' - 5 days) and (5) at the time of treatment discontinuation.

- *T cell activation marker assay* PD-1⁺ CD11a^{high} CD8⁺ T cells will be stained with antibodies for CD69, CD25, CD45RO and CD62L which are upregulated upon T cell activation.
- *T cell proliferation assay* The proliferation of PD-1⁺ CD11a^{high} CD8⁺ T cells will be measured by their larger forward light scatter (FSC) and intranuclear expression of Ki67.
- *T cell differentiation assay* The expression of transcription factors that controls T cell differentiation into effector or memory cells will be analyzed. We will measure the levels of T-bet (for effector T cells) and Eomes (for memory T cells) in PD-1⁺ CD11a^{high} CD8⁺ T cells.
- *T cell function assay*. Cytotoxic (CTL) T cell effector functions of CD11a^{high} PD-1⁺ CD8⁺ T cells will be assessed by measuring degranulation (CD107a expression) and intracellular production of IFN-gamma following a 4-hour *ex vivo* stimulation with PMA/ionomycin or with any known prostate antigen peptides. The expression of effector molecule of CTL (granzyme B) and its inducer transcription factors (Bcl6 and Runx3), will be examined in PD-1⁺ CD11a^{high} CD8⁺ T cells.

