1. BACKGROUND AND RATIONALE

1.1 Cancer of unknown primary (CUP) is an area of unmet need

In the U.S., approximately 31,430 cases of CUP are diagnosed per year (ACS, 2015). CUP is defined as biopsy-proven metastasis in the absence of an identifiable primary site. While no standard 1st-line regimen exists, platinum-, taxane-, or gemcitabine-based therapies, such as carboplatin/paclitaxel, are most commonly used. In clinical trials, including those led by Mayo (Holtan et al., 2012; Yoon et al., 2016), median overall survival (OS) from standard first-line therapies is 7-12 months. OS in the 2nd-line setting is 3-5 months.

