2.1.3 Correlative/Exploratory Objectives

- Evaluate the association of MSI status and mutation load with clinical efficacy
- Evaluate the association of tissue PDL1 expression with clinical efficacy
- Evaluate the association of soluble PD-L1 with clinical efficacy
- Evaluate changes in the CD11a^{high} PD-1^{high} CD8+ T effector population in association with pembrolizumab-based therapy
- Evaluate changes and predictive value of BIM expression in T cells in circulation and the predictive value of BIM/PD-1 expression in tumor infiltrating lymphocytes
- Evaluate the prognostic and predictive value of tumor tissue of origin testing

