3. ELIGIBILITY CRITERIA

3.1 Inclusion Criteria

Subject must meet all of the following applicable inclusion criteria to participate in this study:

1. Written informed consent and HIPAA authorization for release of personal health information prior to registration. **NOTE:** HIPAA authorization may be included in the informed consent or obtained separately.
2. Age \geq 18 years at the time of consent.
3. ECOG Performance Status of \leq 2 within 28 days prior to registration.

4. Archival tissue must be available and identified during screening and shipped prior to Day -21. If archival tissue is not available and the subject is not undergoing a standard of care biopsy, the subject must undergo a research biopsy to obtain fresh tissue prior to start of treatment.
5. Carcinoma of unknown primary after the following diagnostic procedures have been performed if clinically indicated and are unrevealing of the primary site:
 - Complete history and clinically appropriate physical
 - CT scan of chest, abdomen, and pelvis
 - Directed evaluation of symptomatic areas
 - Mammogram in women
 - Colonoscopy in patients with liver metastasis or an elevated CEA
 - Direct pathologic comparison with prior tumor specimens, where possible, even if prior tumor is early-stage or clinically remote from current disease

NOTE: Immunohistochemical stains will be performed according to institutional standards. If a primary carcinoma is identified, the patient should undergo treatment as appropriate for that primary tumor and not be enrolled in the study. The above diagnostic workup does not need to be performed if: (1) it was previously completed at the time of original diagnosis or (2) the investigator does not believe the workup has clinical utility at the current time, given that the patient has received interval therapy.

6. Histologic confirmation of metastatic adenocarcinoma, poorly differentiated non-small cell carcinoma, or poorly differentiated squamous carcinoma. **NOTE:** Pathology consultation at Mayo Clinic is recommended if clinically indicated. One scenario is where unknown primary is the most likely diagnosis but immunostains show relatively site-specific marker staining (e.g., CD45, TTF1, chromogranin, GATA3, PAX8, PSA, melanocytic markers). Information provided for pathology consultation should include recent H&P and imaging reports.

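### The T-cell function assay in Section 8.3.4 allows prostate antigen peptides as an alternative stimulus, which would be uninformative for most patients with carcinoma of unknown primary, and gives no rule for choosing between stimuli or keeping them apart

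*Combined protocol and SAP*

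**What the plan says.** Section 8.3.4 describes four laboratory assays on the CD11a-high PD-1-positive CD8+ T cells: activation, proliferation, differentiation and function. For the fourth, cytotoxic function "will be assessed by measuring degranulation (CD107a expression) and intracellular production of IFN-gamma" after a 4-hour ex vivo stimulation "with PMA/ionomycin or with any known prostate antigen peptides". Blood is drawn at five time points: before Day -21, before each of Cycles 1, 2 and 3, and at treatment discontinuation.

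The same section explains why this cell population was chosen. A new method, it says, "is necessary in situations where the identity of tumor antigens are unknown or suboptimal to be detected by tetramers". The exploratory objective in Section 2.1.3 is to evaluate changes in this "T effector population in association with pembrolizumab-based therapy".

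On the population, Section 1.1 states that "CUP is defined as biopsy-proven metastasis in the absence of an identifiable primary site". Section 3.1 adds: "If a primary carcinoma is identified, the patient should undergo treatment as appropriate for that primary tumor and not be enrolled in the study". Women are eligible; the diagnostic work-up in Section 3.1 lists "Mammogram in women".

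**The concern.** A peptide stimulus reveals tumour-directed function only if the patient's tumour carries the antigens from which the peptides are drawn. In a trial defined by the absence of a known primary, there is no reason to expect prostate antigens in most tumours. A low readout after prostate peptides would then say little about the patient's anti-tumour response, yet it could be recorded as low T-cell function.

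The word *or* adds a second problem. PMA/ionomycin activates T cells without any antigen, so it measures the total capacity of the cells to respond. Peptides measure recall of particular antigens. (This distinction is general assay knowledge; the documents do not state it.) If the stimulus differed between patients or between draws and the results were pooled, a change of reagent could pass for a change over time, which is what the objective sets out to study.

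**Working it through.** No design figure applies to this assay, so the check sets the texts side by side and then bounds the number of samples.

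**Does the stimulus fit the population?**

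- Stimulus (Section 8.3.4): PMA/ionomycin or prostate antigen peptides.
- Population (Sections 1.1 and 3.1): no identifiable primary; a patient with an identified primary is not to be enrolled; women are included.
- Rationale for the marker (Section 8.3.4): tumour antigens are unknown or poorly detected by tetramers. Section 8.3.5 also accepts that antigen specificity cannot be established for the whole T-cell population.
- Justification for prostate peptides in CUP: none in the documents.

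The peptide option therefore does not fit most of the population, and it sits awkwardly with the section's own reason for using a marker that does not depend on knowing the antigen.

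**Is there a rule for choosing or separating the stimuli?** None appears in Section 8.3.4. Section 12.6, which covers the translational analyses, does not mention the stimulus.

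**Where might the wording come from?** Earlier in Section 8.3.4 the patients are described as having gastro-oesophageal junction cancer treated with chemoradiotherapy plus pembrolizumab. Section 8.3.5 refers to immunity against gastric cancer and to draws before surgery and after adjuvant therapy. The treatment plan in Section 5.2 contains no chemotherapy, surgery or adjuvant phase. The prostate wording is most simply read as more text of this kind. It differs from a wrong disease label in one respect: it names a reagent, so following it would change the data.

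**How many samples could be affected?** Count one sample per patient per draw.

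- Inputs: 5 draws (Section 8.3.4); 34 patients enrolled, of whom 29 are evaluable (Section 12.3).
- Formula: samples = draws x patients.
- Ceiling, all enrolled: 5 x 34 = 170.
- Ceiling, evaluable patients: 5 x 29 = 145.
- Floor: 0, if the laboratory uses only PMA/ionomycin.

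The ceilings assume that every patient gives every draw and that peptides are used throughout. The documents do not show where in this range the trial would fall.

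**The case against.** The strongest reply is that the harm is conditional. PMA/ionomycin is named first and works whatever the tumour type. Harm arises only if the laboratory actually uses the peptides, or pools results across stimuli, and nothing in the protocol says that it will. Further assay detail is referred to a Correlative Laboratory Manual, which is not among the documents and may already fix the stimulus. All of this stands, and it is why the floor is zero.

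The reply also limits three stronger conclusions that a reader might draw.

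- *That prostate peptides cannot measure tumour-reactive function in this trial.* Under Section 3.1, PSA staining is an example of a finding that may prompt a recommended pathology consultation; it is not a listed exclusion. Genomic and expression-profiling results are not required before treatment. A few men with an occult prostate origin could therefore be enrolled.
- *That the functional part of the objective will give a wrong result.* Samples stimulated with PMA/ionomycin remain valid as a measure of the subset's capacity. The other three assays in Section 8.3.4 do not use this stimulus.
- *That the planned correlations with clinical outcome are compromised.* Section 12.6 names soluble PD-L1 and T-cell subpopulations as the blood markers. It does not name CD107a or IFN-gamma.

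One could also call this purely editorial, to be tidied up with the other leftover text. The shared origin is likely, but the phrase stands in an operative assay method and permits a choice that would yield uninformative data for most patients. It needs correcting in its own right.

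**Conclusion.** The point holds in a limited form. As written, Section 8.3.4 permits a stimulus that is unlikely to elicit a tumour-specific response in most patients with CUP, and it offers no rule for choosing between two stimuli that measure different things. Samples run with the peptides would be largely uninformative on CD107a and IFN-gamma, and results pooled across stimuli would not be comparable.

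The consequence is minor. It is confined to one of four assays serving an exploratory objective, and Section 12.6 itself treats the translational analyses as exploratory. The primary endpoint, the two-stage design with 14 and then 29 eligible patients, and its error rates are untouched.

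The conclusion rests on two assumptions: that most enrolled tumours are not of prostate origin, for which the documents give no proportion, and that PMA/ionomycin acts without antigen. That the wording was carried over is an inference from the neighbouring text; the conclusion does not depend on it.

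**What to change.** In Section 8.3.4, delete the prostate-peptide option and name PMA/ionomycin as the single stimulus for all patients and all draws. State that the result will be reported as the functional capacity of the CD11a-high PD-1-positive CD8+ subset, not as antigen-specific function.

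If the investigators want a peptide stimulus, they should justify its choice for CUP, run it in addition to PMA/ionomycin, and report it separately without pooling.

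In the same edit, bring the Correlative Laboratory Manual into line and correct the descriptions in Sections 8.3.4 and 8.3.5 that belong to other diseases, treatments and draw schedules.

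The cost is a short text change. The one small downside of using PMA/ionomycin alone is that the assay gives no antigen-specific readout.
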